3.12 Protocol deviation

A protocol deviation is defined as a situation in which there is a non-compliance with the protocol. The following situations are considered protocol deviations and must be appropriately documented:

1. Utilization of another method for guiding the ablation.
2. Ablation of extra PV substrate.

Investigators will be required to adhere to the investigational plan, signed investigator's agreement, applicable national or local, laws and regulations, and any conditions required by the appropriate Ethics Committees or applicable regulatory authorities. The reporting of all the deviations will be performed through the eCRF application. In the event of repeated protocol deviation as determined by the principal investigator, a clinical research associate or clinical representative will attempt to secure compliance by one or more of the following actions: i) contacting the investigator by telephone, or ii) contacting the investigator in writing.

3.13 Harms

Since all included patients must have an indication for AF ablation, no specific harms are expected in the context of the trial, as AI targets will be decreased at those ablation points with lower LAWT values. In fact, in a single-center, prospective series of 80 patients, whose results will be presented at the EHRA 2020 Congress, there were no procedure-related complications using this approach. All complications will be documented as secondary endpoints.

4.2 Responsibilities of the coordinating center

The Heart Institute at Teknon Medical Center (Barcelona, Spain) is the coordinating center that will manage the data and perform statistical analysis.

5. ETHICS AND DISSEMINATION

5.1 Research ethics approval

This protocol must be reviewed and approved by the local institutional review board (IRB) of each center.

5.2 Risks

There are no particular risks related to study participation. Nevertheless, there are risks related to the procedure itself, which is explained on the informed consent sheet.

5.3 Protocol amendments

Any modifications to the protocol which may impact on the conduct of the study, potential benefit of the patient or may affect patient safety, including changes of study objectives, study design, patient population, sample sizes, study procedures, or significant administrative aspects will require a formal amendment to the protocol. Such amendment must be approved by the IRB.

5.4 Consent or assent

Operators will introduce the trial to patients on the pre-operative outpatient visit. Information sheets and consent forms will be provided to all screened patients at the time of the visit and consents will be collected at the time of hospitalization.

5.5 Confidentiality

All study-related information will be stored securely at the study site. All participant information will be stored in locked file cabinets in areas with limited access. All laboratory specimens, reports, data collection, process, and administrative forms will be identified by a coded ID [identification] number only to maintain participant confidentiality. All records that contain names or other personal identifiers, such as locator forms and informed consent forms, will be stored separately from study records identified by code number. All local databases will be secured with password-protected access systems.

5.6 Access to data

Project Principal Investigators will have direct access to their own site's data sets, and will have access to other sites data by request. To ensure confidentiality, data dispersed to project team members will be blinded of any identifying participant information.

5.7 Dissemination policy

The study results will be released to the participating physicians, referring physicians, patients and the general medical community.

APPENDIX 2: Data collection sheet

Name: N° History:

Date of birth: Study code: Center

1. PROCEDURE AND PATIENT DATA

FIRST OPERATOR..... Anesthetist..... EVALUATING OPERATOR.....

DATE OF THE PROCEDURE..... /..... /.....

HR ventilation Yes/No Rate Tidal vol

Age: Sex: Male //Female CHA₂DS₂-VASc = HAS-BLED:... Weight Kg Height: m

CVRF: none // HBP // Dislipemia // DM-2 // Smoker // OSA // Sport (>4 h/week x 10 y)

Underlying HD: none // Hypertensive // Ischemic // HOCM // Valvular // Other

Conduction disturbances: none // LBBB // RBBB // LAHB // LPHB // Other:

Treatment: OAC: Interrupted: Yes // NO // ¿?

TEE LA Size (mm): LVEF: Mitral annulus: cm Other:

PV anatomy: 4 indep. // Left common // Right common // Accessory veins:

LAA Closure: YES // NO Closure device type and size:

2. PROCEDURAL DATA OF PVI:

Number of femoral accesses: 1 / 2 (only 2 permitted in case of ICE use)

Ablation lines adapted to fingerprinted esophagus: YES // NO (why:))

Curve of the ablation catheter (SmartTouch®): Blue // Orange // Black

Procedure time: min FAM + Merge time: min Transeptal time: min

Transeptal puncture technique: TEE // ICE

Fluoro time: sec Fluoro dose: mGy Fluoro dose (index): Gy/cm²

RF power: anterior wall W // posterior wall W

RF time: Right PV s // Left PV s

[figure not shown]
Number of RF points: Left Right

Electrical cardioversion: Yes // No

Acute complications:

Was the procedure evaluated for the absence of gaps by the 2nd operator?: YES // NO

Select at which segment/s the subjacent rhythm was (entirely or predominantly) AF/AT: This is to assess in the future whether segments where rhythm disturbances are observed could influence catheter stability, quality of RF lesions and, ultimately, be a predictor of reconnections.

[figure not shown]
Select at which segment/s **FIRST PASS** isolation was **NOT ACHIEVED**, an explain why:

.....

.....

.....

.....

[figure not shown]
Select at which segment/s **ACUTE RECONNEXION** was observed, an explain why:

.....

.....

.....

.....

APPENDIX 3: Anesthetic protocol for ablation

NOTE: This is a recommended anesthetic protocol, which may be adapted to the daily practice of the corresponding participating centers. The only essential requirement that must be met is to achieve a 'high-rate, low-volume' ventilation: respiratory rate > 40 rpm, and a tidal volume adapted to the patient's weight (in general, 3.5-4.0 ml/Kg).

1. Standard Anesthetic Monitoring:

- Non-invasive blood pressure (NIBP) an invasive blood pressure (IBP)
- EKG
- SpO₂, inspired and tele-expiratory O₂
- Capnography: EtCO₂ and inspired CO₂
- Standard mechanical ventilation monitoring: inspiratory peak pressure, airway plateau pressure, tele-expiratory pressure, tidal volume, respiratory rate, expired volume, pulmonary distensibility curve, arterial gasometry
- Bispectral analysis for anesthetic depth (BIS), neuromuscular relaxation monitoring with train-of-four (TOF-Cuff Monitor®)
- Optional brain Doppler: Peak middle cerebral artery flow (MCA), mean ACM flow and pulsatility index.

2. Anesthetic induction:

Midazolam: 1-2 mg, Fentanyl 2-3 mcg/Kg, Propofol 1.5-2 mg/Kg (holder), Rocuronium bromide: 0.6 mg/kg. It can be considered as anesthetic inducer Etomidate 0.2-0.3 mg/Kg if there is severe ventricular dysfunction or any other reason that contraindicates the use of propofol.

3. Endotracheal intubation:

Once a TOF of 0% is corroborated, endotracheal intubation is performed. It is very important to consider the need to use difficult airway devices (DAV). There is some association between arrhythmias, OSAHS and difficult intubation. On-hand video-laryngoscope (Glidescope®) or similar device for advanced DAV management.

4. Introduction of the Trans-esophageal Echocardiography (ETE) probe:

Standard assessment, corroboration of preoperative data, discard thrombi in left atrial or atrial appendage, left atrial velocity measurement, interatrial septum analysis. Real-time progress guide of catheters and puncture in the appropriate area of the inter-atrial septum. Review of possible complications (rule out hemopericardium, cardiac valvular disease, etc.)

5. Super-Protective Mechanical Ventilation Protocol with Short-Term Permissive Hypercapnia:

Once the patient is intubated, mechanical ventilation is established at Tidal Volume (V_t) of 8 mL/Kg and Respiratory Rate (RR) at 12-15 resp/min, FiO_2 0.5 (oxygen/air) at 1 L/min for 10 min. Alveolar recruitment maneuvers are performed. Then change to the Super-Protective Pattern consisting of V_t 3.5-4.0 mL/Kg and RR 45-55 resp/min; with FiO_2 0.4, I:E relationship 1:1.5, and PEEP 0 mmHg. Systemic blood pressure and pulmonary systolic pressure, RV and LV function, tricuspid valve are evaluated. If there are no changes greater than 10% of baseline values, continue with Super-Protective protocol. If $PaCO_2$ greater than 60 mmHg is documented, a high flow of fresh gases (O_2/FiO_2 air 0,5 to 4 L/min) is administered to increase CO_2 washing of the anatomical dead space. At the end of the Super-Protective protocol, alveolar recruitment maneuvers are performed before anesthetic awakening.

Pre-operative relative contraindications to initiate the Super-Protective protocol:

- Severe LV or RV dysfunction
- Severe pulmonary hypertension
- Moderate or severe CPOD with evidence of self-PEEP
- Severe asthma
- Chronic or severe metabolic acidosis
- Hypercalcemia
- Past history of severe migraines, neuralgia of trigeminal or atypical facial pain, hydrocephalus, patients with ventricular-peritoneal shunt valves, Parkinson's, epilepsy, vertigo, Ménière syndrome, narrow angle glaucoma, or stroke with considerable neurological sequelae.

6. Maintenance of general anesthesia:

Mixture of O_2 /air to FiO_2 0.4 to 4 L/min, Sevoflurane 1-1.5Vol% or propofol 2 mcg/mL TCI (Schnider Model), Remifentanyl 1.5-2.0 ng/mL TCI (Model Minto), Rocuronium 0.2 mg/Kg every 30 minutes.

If PAIV decreases more than 20% with respect to the anesthetic pre-induction value, vasopressor boluses such as: Ephedrine 5-10mg, Phenylephrine 25-50 mcg or Norepinephrine 2.5-5 mcg can be used.

It may be advisable to prepare phenylephrine perfusion at 0.1-0.5 mcg/Kg/min (10 mg in 100 mL of 0.9% sol) to maintain perfusion pressure in case of hypotension. Alternatively, very diluted Noradrenaline ("Baby-Nora": 4 mg/250 mL) infusion of 0.02-0.08 mcg/Kg/min can be used.

7. Anesthetic weaning:

After the TEE is removed (according to echocardiography protocol, after complications of interventional cardiological procedures or other types of incidence have been ruled out), gleras are gently aspirated and a state of residual muscle relaxation is corroborated. The safety target for reversal of neuromuscular relaxation is a 100% TOF, in case the patient presents TOF-ratio less than 80%, Sugammadex 2 mg/Kg is administered. If TOF-ratio is greater than 80% and less than 100% it can be considered to use Sugammadex or neostigmine at 50 mcg/Kg. Paracetamol 1 g, dexketoprofen 50 mg and ondansetron 4 mg is given.

Once the patient has spontaneous breathing, adequate Vt and RR, SpO₂ above 98% and BIS above 80-90, is extinguished. It is transferred to a Semi-Critical Care Unit monitored or with nasal cannulas with FiO₂ 0.3 at 2 L/min.

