2. HYPOTHESIS AND OBJECTIVES

2.1 Research hypothesis

Personalized AF ablation using the ‘*ablation-by-LAW*’ protocol that uses point-by-point adapted AI values according to the local MDCT-derived LAW_T, is feasible, safe and at least as effective as the current AF ablation standards.

Ablation-by-LAW involves the use of tailored point-by-point AI values according to the local MDCT-derived LAW_T, the use of a single-catheter strategy, and the integration of a MDCT-derived ‘fingerprinted’ esophagus image to modify the ablation lines aiming to avoid too close RF applications, while performing the procedures using general anesthesia and a high-rate, low-volume ventilation protocol. The following diagram constitutes a general overview of the protocol:

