3.3 Eligibility criteria

Patients will only be recruited if they fulfill the following inclusion criteria:

- Age > 18 years.
- Indication for paroxysmal atrial fibrillation ablation.
- Signed informed consent.

Patients will be excluded if they meet any of the following exclusion criteria:

- Age < 18 years.
- Pregnancy.
- Previous AF REDO procedure.
- Impossibility to perform a MDCT scan.
- Concomitant investigation treatments.
- Medical, geographical and social factors that make study participation impractical, and inability to give written informed consent. Patient's refusal to participate in the study.

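### Appendix 3 makes high-rate, low-volume ventilation mandatory but lists relative contraindications to it; eligibility does not screen for them and no exemption is stated

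*Combined protocol and SAP*

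**What the plan says.** **Requirement.** The note opening Appendix 3 describes the anaesthetic protocol as recommended and open to local adaptation, with one exception: "The only essential requirement that must be met is to achieve a" high-rate, low-volume pattern. It specifies "respiratory rate > 40 rpm, and a tidal volume adapted to the" patient's weight, "in general, 3.5-4.0 ml/Kg". Section 2.1 describes ablation-by-LAW as "performing the procedures using general anesthesia and a high-rate, low-volume ventilation protocol".

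**Limits on the same pattern.** Item 5 of Appendix 3 sets the Super-Protective pattern at 3.5-4.0 mL/Kg and 45-55 breaths per minute. After the switch, haemodynamics and cardiac function are checked: "If there are no changes greater than 10% of baseline values, continue with Super-Protective protocol". A list then follows, headed "Pre-operative relative contraindications to initiate the Super-Protective protocol". It includes severe left or right ventricular dysfunction, severe pulmonary hypertension, severe asthma, epilepsy and a history of severe migraine.

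**Eligibility.** Section 3.3 names none of these conditions. Its one exclusion tied to a study procedure is "Impossibility to perform a MDCT scan". A general exclusion covers medical, geographical and social factors that make participation impractical. Section 3.9 enrols eligible, consenting patients consecutively.

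**Risk.** Section 5.2 states: "There are no particular risks related to study participation". It adds that the procedure has its own risks, explained on the consent sheet. Section 3.13 expects no specific harms, because Ablation Index targets are lowered where the wall is thin.

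**The concern.** The trial makes a ventilation setting compulsory, and its own appendix says that some patients are relatively unsuited to it. For such a patient, an anaesthetist who follows the note cannot act on the list, and one who acts on the list departs from the only compulsory part of the protocol. The same problem arises during the procedure if the 10% check fails.

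What is at stake is patient safety and consistency between sites. Centres are left to settle the contradiction themselves and may do so differently. An ethics committee reading sections 3.13 and 5.2 would not learn that a study requirement carries a list of contraindications.

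**Working it through.** The plan gives no figure to reproduce on this point, and no sample-size or error-rate formula applies. The check sets the texts side by side.

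1. **Are the required setting and the contraindicated pattern the same?** The note requires more than 40 rpm and in general 3.5-4.0 ml/Kg. Item 5 uses 45-55 per minute and 3.5-4.0 mL/Kg. The tidal volumes are identical and the whole 45-55 range lies above 40, so item 5 delivers the requirement. The only difference is that whole-number rates of 41-44 meet the note but fall outside the item 5 pattern. Nothing in the text offers those rates as an alternative for listed patients.

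2. **Which text takes precedence?** The note makes the appendix adaptable except for the ventilation requirement. The contraindication list and the 10% check therefore sit in the adaptable part, and the requirement does not. On the note's own ranking, the compulsory item stands above the list that would limit it.

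3. **Does eligibility remove the conflict?** The list has six bullets with one entry each (left or right ventricular dysfunction counted once) and a seventh with 11 (migraine, trigeminal neuralgia, atypical facial pain, hydrocephalus, shunt valve, Parkinson's, epilepsy, vertigo, Ménière syndrome, glaucoma, stroke sequelae). That makes 6 + 11 = 17 conditions. Section 3.3 names 0 of the 17.

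4. **Is there an exemption?** None appears in section 2.1, in section 3.4.3 (which sends the reader to Appendix 3), in the note or in item 5.

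5. **What happens if the 10% check fails?** Item 5 gives an action for PaCO2 above 60 mmHg but none for a change above 10%. The wording implies that the pattern need not continue. The note still requires it, and no compliant alternative is described.

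6. **Do the risk sections cover this?** Section 3.13 reasons from Ablation Index targets only. It cites a single-centre series of 80 patients without procedure-related complications, but does not say whether any of them had a listed condition. Section 5.2 does not mention ventilation. Item 5 is titled as a protocol with short-term permissive hypercapnia.

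7. **How many patients?** The documents give no frequency for any listed condition or for failure of the 10% check, so no count out of the planned 106 can be derived.

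**The case against.** The strongest reply is that the text leaves more room than the note suggests.

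- **The contraindications are relative.** This stands: nothing is absolutely barred. It moves the contradiction without removing it, because relative means that someone weighs the case, and a requirement that must be met leaves nothing to weigh.
- **Section 3.3 has a general medical-factors exclusion.** A site could use it, so a reader who infers that every listed patient must either be ventilated against the list or become a breach goes too far. But that criterion concerns impracticality and refers neither to ventilation nor to the list.
- **The Appendix 2 data sheet has a Yes/No item for high-rate ventilation.** Non-use can therefore be recorded. Recording it does not permit it, and the item asks no reason.
- **Ventilation is a condition of the procedure, not a core element.** The closing paragraph of section 1 names three elements of the personalised protocol, and ventilation is not one. This stands as a reason not to say that a patient ventilated otherwise has missed the intervention. The note's wording is unaffected.
- **Non-use has no stated analytic consequence.** Ventilation is not among the two named deviations in section 3.12, although the general definition there covers any non-compliance. The section 3.10.3 exclusion concerns the wall-thickness protocol, in the context of ablation settings and RF applications. No effect on the primary endpoint follows from the text.

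**Conclusion.** The contradiction is real. Appendix 3 imposes a ventilation requirement without exception and lists relative contraindications to the same pattern. Its 10% check has no branch for failure. Section 3.3 does not specifically exclude the patients concerned, and the general exclusion and the Yes/No item do not settle the matter. Sections 3.13 and 5.2 are silent on it.

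The conclusion rests on the wording alone and needs no assumption about prevalence. The number of patients affected is unknown.

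Three stronger readings are tempting but unsupported:

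- **That the conditions would come to light only at anaesthesia.** The list is headed pre-operative, and section 3.6.1 places medical history, examination and transthoracic echocardiography at enrolment.
- **That patients are told there is no study-specific risk.** The consent sheet is not in the text available for review, and section 5.2 refers to it for procedural risks. The point is limited to what sections 3.13 and 5.2 say.
- **That section 3.3 deliberately enrols these patients.** It only fails to name them. The etomidate option for severe ventricular dysfunction in item 2 is a conditional alternative in a generic, adaptable protocol and does not show that such patients are expected.

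**What to change.** The sponsor's clinical team should reconcile section 2.1, section 3.3 and Appendix 3 (the note and item 5) so that the compulsory requirement, the contraindication list, the 10% check and eligibility agree. The clinical rule is theirs to choose, and none is proposed here. Sections 3.13 and 5.2 should then be brought into line with the result, so that their statements on harms and risks take account of the ventilation requirement.

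The cost is a short protocol amendment, which section 5.3 makes subject to IRB approval because it touches patient safety.

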APPENDIX 4: Representative figures

Figure 1. Aspect of the left atrial (LA) anterior wall after MDCT imaging segmentation. An analysis of the LA wall thickness (LAWT) has been performed. The color map uses a color scale to depict a range of thickness; red being the thinnest (< 1 mm) and purple being the thickest (> 4 mm). Yellow (1-2 mm), green (2-3 mm) and blue (3-4 mm) will be considered the intermediate values. The full-range color-coded LAWT map (*left image*) can be simplified using an adaptive binarization algorithm (*right image*) that helps selection the proper Ablation Index (AI) targets for each zone.

[figure not shown]

Figure 2. Aspect of the LA posterior wall after MDCT imaging segmentation. *Right image:* Full-range color-coded LAWT map as seen in CARTO. *Left image:* Binarized color-coded LAWT map integrated in CARTO.
